7. SAFETY REPORTING

7.1 Adverse Event (AE)

An AE is any untoward medical occurrence in a patient or clinical trial subject undergoing a trial intervention and which does not necessarily have a causal relationship with this treatment. An AE can therefore be any unfavourable and unintended sign (including an abnormal laboratory finding), symptom, or disease temporally associated with the use of the trial interventions, whether or not considered related to the interventions being evaluated.

7.2 Adverse Event recording

For the purposes of the study, AEs will be followed up according to local practice until the event has stabilised or resolved, or the Follow-up Visit, whichever is the sooner. All AEs and

IP7-PACIFIC	Protocol No: 22CX7488	Imperial College London	V3.0 18 th December 2023

SAEs will be recorded throughout the study and all SAES, where in the opinion of the Chief Investigator, the event is 'related' and 'unexpected' should be reported to the sponsor and also be reported to the REC.

(i) Severity of Adverse Events

Mild:Awareness of event but easily toleratedModerate:Discomfort enough to cause some interference with usual activitySevere:Inability to carry out usual activity

(ii) Causality of Adverse Events

Unrelated: No evidence of any causal relationship Unlikely: There is little evidence to suggest there is a causal relationship (e.g. the event did not occur within a reasonable time after administration of the trial medication). There is another reasonable explanation for the event (e.g. the patient's clinical condition, other concomitant treatment).

- Possible: There is some evidence to suggest a causal relationship (e.g. because the event occurs within a reasonable time after administration of the trial medication). However, the influence of other factors may have contributed to the event (e.g. the patient's clinical condition, other concomitant treatments).
- Probable: There is evidence to suggest a causal relationship and the influence of other factors is unlikely.
- Definite: There is clear evidence to suggest a causal relationship and other possible contributing factors can be ruled out.

7.3 Serious Adverse Events (SAE)

(i) Definition of SAE

An SAE is defined as any event that

- Results in death;
- Is life-threatening*;
- Requires hospitalisation or prolongation of existing inpatient's hospitalisation**;
- Results in persistent or significant disability or incapacity;
- Is a congenital abnormality or birth defect;

* "Life-threatening" in the definition of "serious" refers to an event in which the subject was at risk of death at the time of the event; it does not refer to an event which hypothetically might have caused death if it were more severe.

** "Hospitalisation" means any unexpected admission to a hospital department. It does not usually apply to scheduled admissions that were planned before study inclusion or visits to casualty (without admission).

Medical judgement should be exercised in deciding whether an adverse event/reaction is serious in other situations. Important adverse events/reactions that are not immediately life-threatening, or do not result in death or hospitalisation but may jeopardise a subject, or may require intervention to prevent one of the other outcomes listed in the definition above should also be considered serious.

7.4 Reporting of SAEs

Reporting of all SAEs (for exceptions see below), occurring during the study must be performed as detailed in SAE reporting instructions. If the investigator becomes aware of safety information that appears to be related to the trial, involving a subject who participated in the study, even after an individual subject has completed the study, this should be reported to the Sponsor.

All SAEs will be reviewed by the Chief Investigator or a designated medically qualified representative to confirm expectedness and causality.

Reporting of SAEs and review by the CI will be via the trial data collection system (CRF/eCRF).

List of Expected Adverse Events

There are number of expected potential adverse events after interventions that may occur and require hospitalisation but will not require reporting as SAEs but will be collected in the eCRF. These include:

- Gadolinium or buscopan related allergic reactions of any severity
- Claustrophobia leading to abandoning of MRI scan
- Vasovagal fainting episode before, during or after MRI or biopsy
- Urinary retention and any admission required for this
- Urinary tract infection and any admission required for this
- Epididymo-orchitis and any admission required for this
- Dysuria
- Debris in urine and any admission required for this
- Haematuria and any admission required for this
- Erectile dysfunction and any other sexual sequelae side-effects such as dry orgasm, lack of orgasm, poor libido

(i) Related SAEs

Related: resulted from administration of any of the research procedures

(ii) Unexpected SAEs

Unexpected: type of event is not listed in the protocol as an expected occurrence

(iii) Reporting of SAEs that are related and unexpected

SAEs that are *related and unexpected* should be notified to the relevant REC and the Sponsor in accordance with local requirements. Reports of related and unexpected SAEs should be submitted within 15 days of the Chief Investigator becoming aware of the event, using the *NRES SAE form for non-IMP studies*. The Chief Investigator must also notify the Sponsor of all SAEs where in the opinion of the Chief Investigator, the event is 'related' and 'unexpected'. Local investigators should report any SAEs as required by their Local Research Ethics Committee, Sponsor and/or Research & Development Office.

Contact details of sponsor for reporting SAEs are as follows:

The Research Governance and Integrity Team:

Imperial College London and Imperial College Healthcare NHS Trust. Email: [contact]

Chief Investigator: [name] Imperial College London, Charing Cross Campus E-mail: [contact] [contact] (Mon to Fri 09.00 –17.00)

Follow-up of patients who have experienced a related and unexpected SAE should continue until recovery is complete or the condition has stabilised. Reports for related and unexpected SAEs should be unblinded prior to submission if required by national requirements.

(iv) Annual reporting of Serious Adverse Events

Annual Progress reports will be submitted to the Sponsor and the Research Ethics Committee in accordance with local requirements. The Annual Progress Report will detail all SAEs recorded.

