Since biopsies can cause side-effects such as pain, bleeding and infection, a non-suspicious mpMRI can allow some men to avoid an invasive biopsy as the probability of clinically significant prostate cancer is low. In the UK, a decision on whether to carry out a biopsy is then based on the mpMRI findings in combination with other clinical factors: about a guarter can avoid an immediate biopsy due to a low risk of harbouring clinically significant prostate cancer. In most centres, if a biopsy is indicated, it is guided by ultrasound with the operator estimating where to deploy the biopsy needle in order to take tissue samples; what is commonly referred to as visual-registration targeting. We want to test two major changes that might further improve this new pathway.

First, mpMRI takes 40 minutes, requires intravenous gadolinium contrast and costs £239 (NHS HRG 2020 Tariff) in the UK NHS. Administration of gadolinium requires medical supervision due to a risk of anaphylaxis. Further, there is concern about its deposition in the brain although there is uncertainty about whether this causes harm. In addition, many hospitals struggle with scanner time and this can lead to patients with suspected prostate

cancer and other medical conditions waiting longer [Royal of College of Radiology 2017]. A 15 minute, bpMRI that does not involve injection of gadolinium contrast and costs £141 (NHS HRG 2020 Tariff) might be as accurate as mpMRI in ruling-out and detecting clinically significant prostate cancer.

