2.4 Secondary Endpoints

Clinical

In each of the randomised groups, secondary outcomes are:

- MRI and biopsy-related adverse events and serious adverse events
- The proportion of patients advised to undergo a needle biopsy and the proportion of
 patients undergoing a prostate biopsy after MRI. We will document common reasons for
 patients who are advised to undergo a biopsy who decline and reasons for patients who
 are advised against a needle biopsy who still choose to have a biopsy. We shall record
 the number of patients with a non-suspicious bpMRI/mpMRI that are recommended for
 biopsy and the types cancers subsequently detected.
- The proportion of patients diagnosed with clinically insignificant prostates cancers, defined as any Gleason 3+3=6 on needle biopsy carried out after MRI. These will also be stratified by MRI score, presence of clinical risk factors and whether the biopsy was carried out on clinician recommendation or patient choice.
- The proportion of patients diagnosed with clinically significant and clinically insignificant prostate cancers using other histological thresholds, on prostate biopsy carried out after MRI. Similarly, as above, we will also evaluate these proportions by MRI score at patient and lesion level (on a scale of 1 to 5) and by presence or absence of clinical risk parameters.

- The proportion of patients diagnosed with clinically significant and clinically insignificant prostate cancers using all histological thresholds on targeted biopsy using 4 targeted cores only compared to 6 targeted cores for the first targeted lesion.
- Detection rates for each randomised group of known prognostic risk categories. These are D'Amico, National Comprehensive Cancer Network (NCCN) and Cambridge Prognostic Groups (CPG).
- A comparison of the two MRI scoring systems, Likert and PIRADS [latest version as defined in MRI Reporting SOP], in terms of the proportion of patients biopsied and subsequently diagnosed with clinically significant and clinically insignificant prostate cancer, using each of the histological thresholds, on a prostate biopsy. Our study would be an opportunity to conduct a robust comparison of the two reporting systems in a large sample and allow inclusion in meta-analyses with studies that used either one alone.

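### Section 7.4 exempts contrast allergic reactions of any severity from SAE reporting, which conflicts with the section 7.3 definition when such a reaction is fatal or life-threatening

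*Protocol*

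**What the plan says.** Protocol section 7.3 defines an SAE by outcome. Death, immediate risk of death, hospitalisation, and lasting disability or incapacity each make an event serious, with no exception by type of event.

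Section 7.4 sets the reporting rule: "Reporting of all SAEs (for exceptions see below), occurring during the study must be performed as detailed in SAE reporting instructions". The exceptions are a list of ten expected events, introduced as ones that "may occur and require hospitalisation but will not require reporting as SAEs but will be collected in the eCRF". The first item is "Gadolinium or buscopan related allergic reactions of any severity".

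The same section defines expectedness: "Unexpected: type of event is not listed in the protocol as an expected occurrence". SAEs that are both related and unexpected "should be notified to the relevant REC and the Sponsor in accordance with local requirements", within 15 days of the Chief Investigator becoming aware.

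Two other places show why this item matters here. The background (section 1) states: "Administration of gadolinium requires medical supervision due to a risk of anaphylaxis". Section 2.4 lists as a secondary outcome, in each randomised group, "MRI and biopsy-related adverse events and serious adverse events".

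**The concern.** Sections 7.3 and 7.4 give different answers for the same event. Under 7.3 a life-threatening reaction to contrast is an SAE. Under 7.4 it need not be reported as one, however severe. Sites could reasonably apply the two sections differently.

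At stake first is oversight. A fatal or life-threatening reaction to a study procedure could pass without an SAE report and without an expedited notice to the ethics committee and sponsor.

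Second is the comparison of the MRI arms. Gadolinium is what mpMRI adds to the bpMRI sequences (section 5, Randomisation 1), so gadolinium reactions fall in one arm. If SAE tables were built from reported SAEs, the exemption would lower the count in the mpMRI arm only and pull the comparison towards no difference, to the disadvantage of bpMRI.

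**Working it through.** No figure in the protocol needs reproducing. The check is to take one hypothetical event, a life-threatening allergic reaction to gadolinium, through the rules in order.

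1. **Is it an SAE?** Yes under section 7.3, because the patient was at risk of death at the time.
2. **Must it be reported as an SAE?** Not under section 7.4. It is on the list of exceptions, and the item carries no cap on severity. It is the only one of the ten items with such a clause. Five items (urinary retention, urinary tract infection, epididymo-orchitis, debris in urine, haematuria) extend the exemption to an admission for the event. The other four (claustrophobia, vasovagal episode, dysuria, sexual side-effects) mention neither severity nor admission.
3. **Is it unexpected?** No. Section 7.4 asks only whether the type of event is listed. Severity and outcome do not enter.
4. **Does it reach the 15-day route?** No. That route needs related and unexpected together, and step 3 fails.
5. **Does another clause bring it back?** Sections 7.2 to 7.5 contain no explicit override for death or risk of death. Section 7.2 says all AEs and SAEs are recorded, but limits onward reporting to related and unexpected SAEs. Section 7.5 applies only once urgent safety measures have been taken.
6. **Can it be recovered from the data?** Probably, since listed events go into the eCRF. But the severity scale in section 7.2 ends at inability to carry out usual activity and has no life-threatening or fatal grade. Severity alone would not separate anaphylaxis from a lesser severe reaction; the section 7.3 criteria would have to be recorded for listed events too.

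**Illustration only.** 3600 patients randomised 1:1 give 3600 / 2 = 1800 in the mpMRI arm. At an assumed rate of serious contrast reactions of 1 in 1000, 1800 × 0.001 = 1.8 events would be affected; at an assumed 1 in 200, 1800 × 0.005 = 9. Neither rate comes from the protocol.

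**The case against.** The strongest reply is that section 7.4 governs reporting, not classification or data capture. It leaves the section 7.3 definition intact, section 7.2 requires all AEs and SAEs to be recorded, listed events are collected in the eCRF, and section 5 gives every patient a questionnaire on MRI side-effects. The secondary endpoint covers adverse events as well as serious ones. The annual progress report is to detail SAEs recorded, which can be read to include an exempted reaction. All of this stands.

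A reader might therefore infer too much in three ways:

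- *That serious contrast reactions are removed from the SAE endpoint by rule.* No section says the endpoint tables use only reported SAEs. The understatement is conditional on the tables being built that way.
- *That the monitoring committee would not be told.* Section 11.3 gives it the task of monitoring the data and does not restrict it to reported SAEs. Its charter is a separate document.
- *That the exemption as a whole concerns a difference between arms.* This is shown for gadolinium only. The protocol does not present buscopan as differing between arms.

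It can also be argued that the exemption is narrower than it looks. The lead-in speaks of hospitalisation, and severity in section 7.2 means mild, moderate or severe, which is distinct from seriousness. That reading is possible, but the text does not state it, and the type-only definition of unexpected points the other way. The separate SAE reporting instructions, the duty to tell the sponsor of safety information that appears related to the trial, and local requirements leave other routes open. None is an explicit override.

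**Conclusion.** The point holds as a conflict between two stated rules. As written, a fatal or life-threatening reaction to gadolinium or buscopan is an SAE under section 7.3, yet need not be reported as one and fails the test for the 15-day route under section 7.4. This rests on the absence of any override in sections 7.2 to 7.5; the SAE reporting instructions and the committee charter were not available.

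The effect on the by-arm SAE comparison is conditional: it arises only if that comparison uses reported SAEs instead of all eCRF events that meet section 7.3. Its direction would then be to understate SAEs in the mpMRI arm. Its size cannot be derived from the protocol. Patients with an absolute contraindication to gadolinium are excluded, so the number is probably small, and a single unescalated event is the main concern. The change is worth making because it is cheap and concerns the contrast risk that the protocol itself names.

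**What to change.** Reconcile sections 7.3 and 7.4:

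- Limit the exemption to listed events that are serious solely through hospitalisation. Listed events that are fatal, life-threatening or disabling stay reportable as SAEs.
- State whether expectedness depends on severity and outcome as well as type. Otherwise a fatal listed reaction, although reportable again, would still count as expected and miss the 15-day route.
- Record the section 7.3 criteria in the eCRF for every listed event. Tabulate all listed events that meet them as SAEs by arm, both in the secondary endpoint and in the reports to the monitoring committee.

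The cost is a short amendment, a check that the eCRF captures seriousness for listed events, and very few additional reports. SAE reporting already runs through the CRF/eCRF system, so no new reporting channel is needed.

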7.5 Reporting urgent safety measures

If any urgent safety measures are taken the CI/Sponsor shall immediately and in any event no later than 3 days from the date the measures are taken, give written notice to the relevant REC of the measures taken and the circumstances giving rise to those measures.

8. STATISTICAL ANALYSES

8.1 Sample Size and power considerations

Randomisation 1: bpMRI vs mpMRI

Consistent with NIHR-HTA PROMIS [[name] et al, 2017], NIHR PRECISION observed a 38% detection of clinically significant prostate cancer (defined as any Gleason >/=3+4 [ISUP Grade Group >/=2]) in patients with suspected prostate cancer having pre-biopsy mpMRI compared to 26% having a traditional biopsy alone without pre-biopsy MRI [Kasivisvanathan et al, 2018]. To preserve at least 50% of the improvement in detection rates implies exclusion of a 6% absolute reduction from a 38% detection rate in order to recommend a switch from mpMRI to bpMRI. We have chosen a non-inferiority margin of 5% which strikes a balance between our clinician survey, the patient perspective, ensuring improvement on the previous standard of care and an achievable sample size. To provide 90% power to confirm non-inferiority and exclude an absolute 5% reduction in detection rate of clinically significant prostate cancer from an estimated 38% in both arms, using an overall 0.05 significance level for a one-sided test, requires 3230 men (1615/arm). A target sample size of 3600, would therefore account for an assumed attrition rate of about 10%.

IP7-PACIFIC Protocol No: 22CX7488	Imperial College London	V3.0 18 th December 2023
-----------------------------------	-------------------------	-------------------------------------

The expected detection rates of clinically significant prostate cancer (defined as any Gleason >/=3+4 [ISUP Grade Group >/=2])are 55% (visual-registration) and 65% (image-fusion). Our clinician and patient groups indicated that >/=10% improved detection rate using image-fusion is acceptable for adoption. In PRECISION and PROMIS, approximately 70-75% were recommended for biopsy following mpMRI. Assuming 70% will be recommended for biopsy and conservatively assuming a further 10% attrition, we anticipate at least 2000 patients from randomisation-1 would be eligible for randomisation-2. This provides ample power (>95%) to detect the absolute 10% difference described above using a two-sided test at the 5% significance level. Include the number of subjects to be enrolled, reason for choice of the sample size, including details of the sample size estimation and the power of the study and clinical justification.

8.2 Planned recruitment rate

With up to 30 recruiting centres (up to 10 pilot centres initially for 12 months and all remaining sites then recruiting for a further 18 months), we would expect to comfortably meet our target of 3600, even if the patient acceptance rate was as low as half the 60% reported in the PRECISION RCT [5].

8.3 Statistical Analysis

Interim monitoring & internal pilot

We will monitor recruitment, statistical assumptions and safety at 6 months and formally review 12 months recruitment into the internal pilot. During the first 12 months, our targets are for gradual opening of at up to 10 centres (although more can be opened if possible), 700 recruited for randomisation-1 and 400 for randomisation-2. At this stage, stopping guidance will be based on ability to recruit, and on discussion with the independent trials steering committee.

Our independent data monitoring committee will provide stopping guidance based on interim futility or demonstrated superiority analyses when at least 50% of our overall sample size for randomisation-1 has provided primary outcome data. They will also consider the underlying assumptions for randomisation-2 and make recommendations regarding continuation of randomisation-2 at this point.

We will monitor recruitment, statistical assumptions and safety regularly throughout the trial. There will be an independent Trial Steering Committee (TSC) and Data and Ethics Monitoring Committee (DMEC). The first 12 months of recruitment will be an internal pilot with an emphasis on ability to recruit, with targets at this stage being 700 patients recruited from at least 10 centres and obtaining primary outcome data on 80% of all participants randomised up to 4 months prior to data-extraction (accounting for expected timeframe: 3 months for conduct of MRI and biopsy and histology results to be made available followed by up to 30 days to transfer data to the database).

Proposed length of internal	I pilot phase: 12 month	S
-----------------------------	-------------------------	---

Pilot Trial Targets Red Amber Green

IP7-PACIFIC Protocol No: 22CX7488	Imperial College London	V3.0 18 th December 2023
-----------------------------------	-------------------------	-------------------------------------

% Recruitment threshold	<50%	50 - 99.9%	≥100%
Recruitment rate / site / month	2.8	2.9-5.8	≥5.8
Number of sites opened	5	6-9	≥10
Total number of participants recruited	<350	350-699	≥700
% Primary outcome data threshold	<40%	40-80%	≥80%
(all randomised 60 days prior to data extraction)			

In summary, if at least 700 (100%) patients are recruited in the pilot, we would expect the TSC to recommend continuation of the trial (in line with NIHR guidance regarding green threshold). If the pilot recruits less than 350 patients (<50%), then this indicates a recommendation for stopping unless there is a very good reason for delay and a convincing solution can be employed. If the pilot recruits 350-699 (50-99%) then, in discussion with the TSC and funder, measures to improve recruitment may be needed in the main trial. We shall use the % targets (100%, 50-99%, <50%) to inform study management setting site-specific targets, depending on the expected recruitment as declared by each of our pilot sites. We shall monitor site recruitment regularly as part of study management and if sites are underperforming or delayed in set-up, we shall consider opening sites from a reserve list.

Randomisation-2 will be stratified by arm allocated in randomisation-1. Potential effects of co-enrolment are likely small but will be monitored. Comparisons will be adjusted for trial arm of the other trial and if we were to anticipate an increase in SEs by 5% from using adjusted effect estimates, we would maintain an adequate level of power (>80%) in our respective randomised comparisons.

Main study clinical outcomes analysis

For each randomisation, the number and proportion of clinically significant cancers detected in the randomised population will be reported by trial arm. Group differences will be quantified by the risk difference with two-sided confidence intervals at a level appropriate to the significance level pre-specified in the sample size. Detection rates will be compared by trial arm using mixed models with adjustment for trial arm allocation of co-enrolled trial and random effect by centre. The treatment effect coefficients will be presented with confidence intervals and associated p-value. The primary analysis will be conducted on an intention-totreat (ITT) basis, where patients with missing outcomes are assumed not to have clinically significant prostate cancer. A modified ITT analysis will be performed excluding patients who did not complete the diagnostic tests, and for the non-inferiority comparison a per protocol analysis including only those undergoing randomly assigned interventions. A pre-specified statistical analysis plan will be drafted detailing intended analyses for primary and secondary outcomes. It will be approved by the IDMC and agreed prior to analysis.

Cost-effectiveness analysis

A within trial cost-effectiveness analyses will estimate the incremental cost per true positive detected and incremental cost per correct diagnosis. Estimates of diagnostic performance will be based on the trial analysis and costs will be estimated from the NHS and PSS perspective using a micro-costing approach for tests. Deterministic (to explore plausible alternatives e.g., quantity of resources used or unit costs) will be combined with stochastic

IP7-PACIFIC Protocol No: 22CX7488	Imperial College London	V3.0 18 th December 2023
-----------------------------------	-------------------------	-------------------------------------

sensitivity analysis (used to explore statistical imprecision in estimates of costs, effects and cost-effectiveness).

We will also conduct a model-based cost-utility analysis, taking the form of a discrete event simulation as the model will explore the impact of allowing more patients to be imaged and the impact on services later in the care pathway. Stakeholders and literature reviews will inform the structure of the model. Data from the trial and secondary sources such as systematic reviews and other evaluations will be synthesised to build and parametrise the model. As outcomes for individuals modelled will occur beyond a 12-month period both health benefits and costs will be discounted using the current recommended rate of 3.5% for both costs and benefits [34]. The time horizon will be the patients' remaining life-years. The results will be reported as total costs, total QALYs and incremental costs per QALY. Both probabilistic and deterministic sensitivity analysis will be conducted.

Justification for an economic evaluation

It is possible that there will be time and other resource saving with bpMRI compared with mpMRI and hence the delivery and interpretation of bpMRI may be less costly than mpMRI. An earlier NIHR-HTA report from 2013 by Mowatt and colleagues [2013] estimated a range of timings per patient with ~12minutes difference between bpMRI and mpMRI. These estimates are applicable to the process of MRI prior to 2013 and before the NIHR-HTA PROMIS and NIHR PRECISION studies reported in 2017. Furthermore, these estimates are not based upon direct observation across a range of centres working with different scanner makes and models (an issue highlighted in recent work in work by Prostate Cancer UK, https://prostatecanceruk.org/media/2496787/mpmri-imaging-guidance-document-final.pdf). In this work, in comparison to the earlier work by Mowatt and colleagues, our estimates of the costs of the diagnostic tests will be based on a micro-costing approach using patient level data. The costs used by Mowatt and colleagues were based on expert opinion from the very small number of clinicians involved in the study and are now over ten years old. The prospective nature of our proposed multicentre study should provide more up to date, precise and transferable data applicable to NHS practice.

Our proposed study design is a non-inferiority study. However, it is only non-inferior with respect to the primary outcome and one form of imaging may be superior in other aspects (for example one form of imaging may be less costly). It is possible that even though the study is designed to be a non-inferiority study that clinically important differences may not be ruled out by the final analysis. To mitigate against this possibility and still provide information to guide NHS-decision making we propose to conduct (as described below) a cost-utility analysis.

The proposed economic evaluation work described below will also allow us to consider whether the resource implications of adopting a potentially less time-consuming imaging methods as well as any knock-on effects elsewhere in the system caused by changes in the imaging process.

Within trial analysis

A within trial cost-effectiveness analyses will estimate the incremental cost per true positive detected and incremental cost per correct diagnosis. Estimates of diagnostic performance will be based on the trial analysis and costs will be estimated from the NHS and PSS perspective. The costs of the tests will be based upon a micro -costing approach for tests. Costs components will include cost of staff time to deliver and interpret the tests. In sensitivity analysis we will also consider the additional costs of training additional health

personnel, and the time spent in familiarising with the technology. Data on the resources needed to deliver and interpret the tests will be collected via a case report form and from study centres. Other care provided up to the end of the trial follow-up will also be collected via a case report form.

Unit costs of these resources will come from study centres and routine data sources (e.g. salary scales, etc). These unit costs will be combined with resource use to estimate the cost for each trial participant. Regression techniques will be applied to data on total costs to determine any difference between the two testing strategies. We will assume effects (clinically significant cancers detected) are the same when the estimates of effects (including the extremes of a confidence interval) rule out a minimally important question. In this case, we will present the results as a cost-minimisation analysis. However, if the confidence intervals do not rule out a minimally important difference, we will conduct a formal cost-effectiveness analysis. This will incorporate a stochastic analysis to explore statistical imprecision in the estimates of costs, effects and cost effectiveness. The results of this will be presented as cost and effect plots and cost-effectiveness acceptability curves. Further deterministic sensitivity analysis will be conducted to explore plausible alternatives e.g. around the quantity of resources used or unit costs.

Model based analysis

The model based analysis will be required to explore the impact of two different features: (i) changes in the number of patients who can be imaged as a result of possible reductions in imaging time; (ii) estimation of long-term impacts should clinically important differences not be ruled out. For (i) the focus will be on prostate cancer patients as these could also be considered as a proxy for other patients that could benefit for imaging.

For (ii) the results of the within trial economic evaluation if presented as an incremental cost effectiveness ratio will be difficult to interpret as there is no readily accepted threshold values for society's willingness to pay per additional clinically significant cancer detected. Therefore, we will conduct a model-based cost-utility analysis.

For a model addressing both (i) and (ii) the results will be reported as incremental cost per QALY gained (but see section on resource impact below). Both costs and QALYs will estimated over the estimated patient lifetime. As outcomes for individuals modelled will occur beyond a 12-month period both health benefits and costs will be discounted using the current recommended rate of 3.5% for both costs and benefits at the base case [NICE Guideline, 2013].

We anticipate a Discrete Event Simulation (DES) [Karnon et al, 2012] will be used as the model will explore the impact of allowing more patients to be imaged to determine the long-term impact on services later in the care pathway. However, the precise form of the model will be developed during the course of the study to best address the decision problem and we shall draw upon the advice of the clinical study teams and PPI Group. The model structure is likely to include a short-term decision tree element where that mirrors the within trial analysis and reports costs and outcomes up to the management decision following imaging e.g. biopsy or not. The model will then extrapolate the impact on patients' health (measured in QALYs) and NHS and PSS costs as a consequence of that decision. This will include the impact of 'incorrect or sub-optimal' decisions and the impact of correct decisions. The model will include subsequent treatment/management of prostate cancer, and the impact of recurrence or progression and subsequent management.

Stakeholders and literature reviews will inform the structure of the model. Data from the trial and secondary sources such as existing systematic reviews, primary evidence and other

IP7-PACIFIC Protocol No: 22CX7488	Imperial College London	V3.0 18 th December 2023
-----------------------------------	-------------------------	-------------------------------------

economic evaluations conducted in the area of prostate cancer research will be synthesised to build and parametrise the model. Costs will include costs of tests and costs after followup, which will include adverse effects of the tests and costs of treatment and management of prostate cancer. These data will come from the trial and from existing sources e.g. NHS reference costs. Data will also include specificity and sensitivity of the tests (from the trial), incidence and risk of progression of the disease (assembled from the literature). The clinical and epidemiological data will be used to calculate path probabilities, combined with EQ-5D utility scores assembled from the literature to allow the estimation of QALYs.

Both probabilistic and deterministic sensitivity (to explore other forms of uncertainty e.g.to explore variations in management, in costs or utility values) analysis will be conducted with the results presented as cost/QALY plots and cost-effectiveness acceptability curves.

Resource impact assessment

As the adoption of the bpMRI may provide some resource savings, we will estimate the resource impacts of adopting bpMRI at scale. This will include the shorter-term impacts on imaging services as well as subsequent impacts on urological cancer services caused by any changes in throughput of patients. These resource impacts (both short-term and long-term) will be based upon findings and estimates from the economic evaluations described above. The NICE guidance and tool for resource impact assessment will be used [https://www.nice.org.uk/About/What-we-do/Into-practice/resource-impact-assessment].

